### **Safety Population**

The safety population is defined as any subject who is enrolled into the study and received study drug.

## 6.0 METHODS OF ANALYSES AND PRESENTATIONS

The following sub-sections would be considered for logical presentation of study data.

### 6.1 Subject Disposition

The number of subjects screened, screen failure, enrolled, study completion status will be summarized. Subjects who discontinued from the study will be summarized and listed by their primary reason for discontinuation. Inclusion/exclusion criteria evaluation will also be listed. Analysis populations will be summarized. Subject disposition will be summarized by dosing cohort.

### 6.2 Protocol Deviations

A protocol deviation is defined as any intentional or unintentional change to, or noncompliance with, the approved protocol procedures or requirements. Deviations may result from the action or inaction of the subject, investigator, or site staff. Examples of deviations include, but are not limited to:

- Failure to adhere to study exclusion and inclusion criteria.
- Failure to comply with dispensing or dosing requirements.
- Use of medications, food, drink, herbal remedies, or supplements that are specifically prohibited in the protocol.
- Missed or out-of-window visits.
- Drug dosing not administered within the time frame specified in the protocol.
- Failure to adhere to test requirements, including vital signs, laboratory tests, physical examinations, PK blood draws, medical history, etc. either tests not done, incorrect tests done, or not done within the time frame specified in the protocol.
- Procedural deviations such as incorrect storage of study drug, failure to update the Internal Consent Form (ICF) when new risks become known, failure to obtain Internal Review Board (IRB) approvals for the protocol and ICF revisions.

Protocol deviations will be identified by the project team prior to database lock. A summary of major protocol deviations will be provided by cohort. All protocol deviations will be listed. Intent-to-treat population will be used as an analysis population for this analysis.

### 6.3 Demographic and Baseline Characteristics

Demographic data and subjects' baseline characteristics at screening will be summarized and listed using descriptive summary statistics for intent-to-treat population. The demographic information of age, gender, ethnicity and race will be summarized by cohort. Apart from that, additional information's of height, weight, primary diagnosis and other parameters such as anatomical location of the intervertebral disc (e.g. L5-S1), Location of herniation (e.g. anterior), etc. as appropriate will also be summarized. All demographic and baseline characteristics will be listed in full.

#### **6.4 Medical History**

An analysis of the medical history (including the symptoms associated with herniated lumbar disc) will be performed at screening. A summary table of medical history conditions by body system and preferred term will be presented by cohort. The table will be sorted in alphabetical order by body system and in decreasing frequency of preferred terms based on total number of reports within each body system. The frequency and percentage of subjects who present at least 1 occurrence of the medical history or concurrent condition will be presented. Medical history will be coded using the most recent version available of the Medical Dictionary for Regulatory Activities (MedDRA). All medical history will be listed. The medical history will be analyzed using intent-to-treat population.

#### **6.5 Prior and Concomitant Medication**

All medications (prescription and over-the-counter, vitamin and mineral supplements, and herbs) and all therapies for disc herniation (including but not limited to physical therapy, acupuncture, epidural injections/selective nerve root block) taken or received by the participant within 1 month of screening and throughout study participation will be included on the concomitant medication. Medications taken for a surgical procedure should also be included.

Prior medication is defined as any medication starting and ending before the first study dose.

Prior and Concomitant medications will be classified using the latest version of World Health Organization Drug Dictionary (WHO drug) and will be summarized by the number and percentage of subjects by anatomical therapeutic chemical classification (ATC) level 2 and preferred term. The table will be sorted in alphabetical order by ATC level 2 and in decreasing frequency of preferred terms based on total number of reports within each ATC level. All prior/concomitant medication will be listed.

Concomitant procedures/therapy, rescue medication details also will be summarized by cohort and listed same as mentioned above. Intent-to-treat population will be used as an analysis population.

#### **6.6 Study Drug Treatment Compliance**

Subjects received a single dose of study drug by intradiscal injection. The injection will be performed under fluoroscopic or computerized tomography (CT) guidance and documented by X-ray or CT scan, as well as in the CRF by the investigator. No other measures of treatment compliance will be used. Study drug administration details will be listed for safety population, full analysis set and per protocol population separately.

#### **6.7 Data Endpoints and Analyses**

The primary objective endpoints analysis and safety endpoints will be performed based on safety population. Full analysis set and per protocol set will be used as the analysis population for secondary and exploratory efficacy endpoints. All the results will be summarized by cohort. Descriptive summary statistics mentioned in the [Section 4.0](#) will be used for the analysis. Comprehensive listings of all data will be presented.

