1 SYNOPSIS

Protocol Title:	Open-label, non-controlled, single-ascending dose study to evaluate safety, tolerability, pharmacokinetics, and exploratory efficacy of KTP-001 in subjects with lumbar disc herniation
Sponsor:	Teijin America, Inc.
Study Phase:	Phase 1/2
Indication:	Herniated lumbar disc
Objectives:	
The primary objective of this study is:
 
 • To evaluate the safety and tolerability of a single intradiscal injection of KTP-001 in subjects with a single herniated lumbar disc. 
The secondary objectives of this study are:
 
 • To determine the pharmacokinetics (PK) of KTP-001 in the serum of circulating blood after intradiscal injection of the study drug. • To determine the presence of anti-KTP-001 antibody in the serum of circulating blood after intradiscal injection of the study drug. 
The exploratory objectives of this study are:
 
 • To explore the pharmacodynamics (PD) of keratan sulfate in the serum of circulating blood after intradiscal injection of the study drug. • To assess changes in pain, neurologic examination, disability, magnetic resonance imaging (MRI) and X-ray assessments, Quality of Life (QOL), and patient global impression of change (PGI-C) scores in subjects receiving study drug.
Number of Sites:	This study will be conducted at approximately 8 sites in the United States.
Study Design:	This study is designed as an open-label, non-controlled single ascending dose study. Twenty-four subjects with a diagnosis of a single herniated lumbar disc will be divided into 4 cohorts of 6 subjects. Dose escalation will begin with a 5 µg intra-disc administration. After all subjects in the first cohort have reached the Week 13 assessment, relevant safety data will be reviewed. If adequate safety and tolerability has been demonstrated, KTP-001 dose escalation will continue in subsequent escalating doses of 15, 50, and 150 µg/disc with safety reviews conducted prior to each dose escalation.
Planned Sample Size:	Approximately 48 subjects will be screened to ensure that 24 subjects are enrolled into this study. Subjects who discontinue from the study after enrollment but prior to receiving study drug will be replaced to ensure that at least 6 subjects are treated in each of the 4 cohorts.

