
	
pending disability claim or litigation related to a back condition/disc herniation.
 
24. Has participated in any clinical study within 30 days prior to screening.
 
25. Has a positive screen for hepatitis B surface antigen (HBsAg), anti-hepatitis C virus (HCV), or anti-human immunodeficiency virus (HIV), or has any active, clinically significant infection.
 
26. Has an elevation of aspartate aminotransferase (AST) and/or alanine aminotransaminase (ALT) ≥ 2 X upper limit of normal (ULN), or a total bilirubin $>$ ULN, or a creatinine ≥ 1.5 X ULN, or any other clinically significant laboratory abnormalities that, in the investigator's judgment, would preclude the subject from participation in the study.
 
27. Has any clinically significant ECG abnormalities at screening.
 
28. Has any contraindication to undergo an MRI or has declared inability to tolerate an MRI.
 
29. Has any condition that would, in the investigator's opinion, limit the subject's ability to complete the study.

Duration of Study:	After a single intradiscal injection of study drug, subjects will be confined to the study facility for the first 24 hours and will be asked to participate in this study for at least 24 months (2 years).
Study Drug:	KTP-001 1.0 mg/vial will be provided as a lyophilized powder in 2.0 mL glass vials. Each vial contains 1.0 mg of KTP-001 drug substance, which will be reconstituted with 0.5 mL of sterile water for injection and then diluted with a buffer solution to administer the required injection dose per 1.0 mL.
Dose and Route of Administration:	A single intradiscal injection of doses 5, 15, 50, and 150 μ g/disc of KTP-001 will be administered intradiscally under fluoroscopic or computer tomography (CT) visualization and guidance after a local anesthetic is administered. The final injection volume per subject will be 1.0 mL. Use of an imaging dye is not permitted for the intradiscal injection.

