## 2.0 STUDY OBJECTIVES

### Primary objective

The primary objective of this study is to evaluate the safety and tolerability of a single intradiscal injection of KTP-001 in subjects with a single herniated lumbar disc.

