### 3.2 Study Treatments and Assessments

KTP-001 is the investigational medicinal product. Neither placebo nor any comparator is used. The proposed clinical dose concentrations for this first in human (FIH) study are 5  $\mu\text{g}/\text{disc}$  (Cohort 1), 15  $\mu\text{g}/\text{disc}$  (Cohort 2), 50  $\mu\text{g}/\text{disc}$  (Cohort 3), and 150  $\mu\text{g}/\text{disc}$  (Cohort 4). KTP-001 1.0 mg/vial will be provided as a lyophilized powder in 2.0 mL glass vials. The injection volume per subject will be 1.0 mL. Each vial contains 1.0 mg of KTP-001 drug substance, which will be reconstituted with 0.5 mL of sterile water for injection and then diluted with a buffer solution to administer the required injection dose per 1.0 mL. Single doses of the proposed clinical dose concentrations will be administered intradiscally at the level of lumbar disc herniation by injection under fluoroscopic or computerized tomography (CT) visualization and guidance to 24 male and female human subjects between the ages of 30 and 70 with a single herniated lumbar disc as confirmed by MRI.

Throughout the study, patients will be assessed for the study objectives as outlined in the schedule of assessments ([appendix 1](#)).

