### **3.4 Sample Size Justification**

No formal sample size calculation was made as no formal hypothesis testing will be performed. The sample size of 24 subjects in 4 cohorts is considered appropriate for a study of this type and was determined by practical considerations. Approximately 48 subjects will be screened to ensure that 24 subjects are enrolled into this study.

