#### 4.0 STATISTICAL CONSIDERATIONS

Statistical analyses will be performed using SAS software, version 9.3 or higher. The safety population will be used as the analysis population for the primary endpoints and all safety end points. Full analysis set and per protocol set will be used as the analysis population for secondary and exploratory efficacy endpoints.

Continuous data will be summarized using n, mean, median, standard deviation (SD), minimum value, maximum value, 95% confidence interval (CI) and, if appropriate, number of missing values. Unless noted otherwise, summaries will be produced by visit (where applicable) and cohort. Summaries by visit will be based on nominal reporting. If more than one value is reported at a scheduled visit, the value collected closest to the intended visit date will be used. In the case of a tie, the latest version will be summarized.

Categorical data will be summarized using n, percentages. Percentages will be calculated based on the number of non-missing values. The number of missing values will be presented as a separate category with no percentage, if 1 or more patients are missing data for the summary. Otherwise, all categories will be presented (even if no patients are counted in the category). Counts of zero in any category will be presented with percentage as (0%).

Precision of summary statistics:

- Integer – Sample size (n, N) and number of missing responses (if displayed).
- One additional decimal place than reported/collected on the case report form (CRF) – mean, median, confidence interval.
- Two additional decimal places than reported/collected on the CRF – standard deviation.
- Same number of decimal places as reported/collected on the CRF – minimum, maximum.
- Percentages – one decimal place.

All data will be presented on listings in order of dosing cohort, patient, assessment date/time and assessment (in order collected on eCRF, unless specified otherwise). For display purposes, cohort labels will be ordered from smallest to largest. Dates will be presented in the format DDMMYY. Times will be displayed in 24-hour clock format. Numbering of tables, figures and listings will follow ICH E3 guidelines.

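### The SAP summarises every endpoint by cohort of six and specifies no all-subject safety summary, so safety features shared across doses are never estimated from all 24 treated subjects.

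*SAP*

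**What the plan says.** SAP 4.0 sets the default: "Unless noted otherwise, summaries will be produced by visit (where applicable) and cohort". SAP 6.7 repeats it for the endpoints: "All the results will be summarized by cohort". A few items name no cohort, for example physical examinations in SAP 6.7.1.7, but they fall under these two rules. Protocol 12.5.1, 12.5.2, 12.7 and 12.9 likewise tabulate by dose level.

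No section specifies a total column, a dose trend or an estimate between cohorts. Two phrases in the SAP could be mistaken for a total. The overall AE summary in 6.7.1.1 is an overview of AE categories. The total number of reports in 6.4 and 6.5 is a rule for sorting rows. SAP 6.7.1.1 also summarises AE intensity and frequency by treatment, which is not defined in a one-drug trial.

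On intervals, SAP 4.0 gives a 95% CI for continuous data but only counts and percentages for categorical data. The protocol synopsis, under safety endpoints and analysis, includes a CI among the statistics for safety endpoints. Those endpoints include AEs, SAEs and the number of subjects with a halting-rule event.

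The primary objective is "to evaluate the safety and tolerability of a single intradiscal injection of KTP-001". On design, the synopsis says: "Twenty-four subjects with a diagnosis of a single herniated lumbar disc will be divided into 4 cohorts of 6 subjects". SAP 3.2 adds: "Neither placebo nor any comparator is used".

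**The concern.** All treated subjects receive the same drug by the same intradiscal route, in the same volume and on the same schedule; only the dose differs. Some safety features should therefore be largely common to the four cohorts, above all those due to the needle, the local anaesthetic and the procedure itself. For such features the natural estimate uses everyone treated.

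The planned tables show four separate six-subject figures. A report built on them has no prespecified rate, and no interval, for AEs, AESIs or halting-rule events over the whole treated group. A pooled figure added later would be a post hoc choice. What is at stake is how precisely the trial can describe its primary endpoint.

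**Working it through.** **Inputs.** Cohorts and size: 4 × 6 = 24, which agrees with the total in SAP 3.4. No alpha, power or effect size is stated ("No formal sample size calculation was made as no formal hypothesis testing will be performed"), so there is no power figure to reproduce. The documents give no SD or event rate, so means are in SD units and the event calculation uses the zero-event case. I assume no dropout.

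**1. Upper limit after zero events** (exact two-sided 95%): 1 − 0.025^(1/n).
- n = 6: 1 − 0.025^(1/6) = 0.459, or 45.9%.
- n = 24: 1 − 0.025^(1/24) = 0.142, or 14.2%.

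**2. The same comparison with events.** One event in every cohort gives the same observed rate (16.7%) at both levels. The exact 95% interval is 0.4% to 64.1% for 1/6 and 4.7% to 37.4% for 4/24.

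**3. Half-width of the 95% CI of a mean change**, in SD units: t(0.975, n − 1)/√n.
- n = 6: 2.571/√6 = 1.05 SD.
- n = 24: 2.069/√24 = 0.42 SD.
- Ratio: 1.049/0.422 = 2.5.

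The figure for 24 applies only if the mean change is common to all four doses.

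**4. If escalation stops early**, the combined group is smaller. With three cohorts the zero-event limit is 1 − 0.025^(1/18) = 18.5%. With two it is 1 − 0.025^(1/12) = 26.5%.

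**5. What a dose slope would add.** On the log10 scale the doses are 0.699, 1.176, 1.699 and 2.176, so the range is 1.477. With six subjects each, Sxx = 7.366.
- 95% half-width of the fitted 150-versus-5 µg difference: t(22) × 1.477/√7.366 = 2.074 × 0.544 = 1.13 SD.
- Direct comparison of the two end cohorts: t(10) × √(2/6) = 2.228 × 0.577 = 1.29 SD.
- Gain: 1 − 1.13/1.29 = 12%, and only if response is linear in log dose.

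**The case against.** The strongest defence is that the omission is inferred from silence. No sentence excludes a total column, the table shells are not in the documents, all data are listed, and Protocol 12.5.9 allows further safety analyses. Cohort is also the natural unit, because the DSMB decides escalation cohort by cohort. A row with four 0/6 cells already lets a reader see 0/24.

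Part of this stands. A reader might infer that the plan throws away most of the trial's precision. The documents do not support that, because a pooled figure can always be derived from the tables and listings. A reader might also infer that cohort tables lower the chance of seeing an event. They do not: that chance depends on how many subjects are treated and followed, not on table layout. The objective's mention of a single injection states how many injections are given; it does not by itself define an estimate pooled over doses.

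The defence does not supply a prespecified combined estimate with an interval. The clause in Protocol 12.5.9 is optional and names no analysis. A total column alone would not be enough either, since SAP 4.0 attaches no CI to categorical data.

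**Conclusion.** The point holds for the safety tables. For features shared across doses, the planned summaries give no estimate from all 24 treated subjects. The upper limit after zero events is 45.9% in a cohort against 14.2% in the whole group, and the half-width of a mean change is 1.05 SD against 0.42 SD. These figures assume four filled cohorts, complete follow-up and, for the mean, an effect common to all doses.

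Two further inferences are tempting and go too far.
- Dose might be called the trial's only internal comparison. It is the only between-subject one, because change from baseline within subjects is planned throughout.
- A dose slope might seem the way to separate drug effect from natural course. The cohorts are sequential and not randomised (SAP 3.1 and 3.3), so dose is confounded with enrolment order, and the slope narrows the end-to-end interval by only about 12%.

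The case also does not extend to pooled efficacy means. An uncontrolled average over a 30-fold dose range, in subjects selected for leg pain, would put a narrow interval around a mix of dose effects, regression to the mean and natural course.

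**What to change.** In SAP 4.0 and 6.7.1, specify the safety tables *by cohort and for all KTP-001 subjects combined*. This covers AEs, SAEs, AESIs, halting-rule events, antibody, imaging, laboratory tests and vital signs. The antibody summary is described in SAP 6.8, so the wording should carry over there.

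Add exact 95% CIs to the AE, SAE, AESI and halting-rule proportions. The protocol synopsis already foresees CIs for safety endpoints. Keep the cohort columns beside the combined one.

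The cost is one column per safety table and an interval on four kinds of count, with no change to data collection. The downside is that the combined column mixes doses, so a footnote should say that it is to be read only alongside the cohort columns.

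A log-dose slope is optional. If the sponsor wants one, it should be labelled exploratory and limited to one named measure at Week 13. It should be given with a 95% CI, no p-value and a statement that dose is confounded with enrolment order.

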### **6.7.1 Analysis of Primary Endpoint - Safety**

Primary endpoint of this study is safety and tolerability. The following are the primary safety endpoints:

- Adverse events (AE)
- Serious adverse events (SAE)
- Deaths or discontinuations due to AEs (including subjects who have lumbar surgery) that occur after administration of study drug.
- Change and shifts from baseline in vital signs of
  - Heart rate
  - Systolic/Diastolic blood pressure
  - Respiratory rate
  - Body temperature
- Tabulation of number of subjects with "substantial" increases or decreases in BP (>20 mmHg) and heart rate (>15 bpm)
- 12-lead Electrocardiograms (ECGs)
  - Heart rate
  - Rhythm
  - PR
  - RR
  - PQ
  - QT intervals
  - QTc [Bazett's and Fridericia's]
  - QRS
- Clinical laboratory tests
  - Hematology
  - Serum chemistry
  - Coagulation
  - Urinalysis
- Data from MRI and X-ray (including morphological assessment)
- Data from neurologic assessments
  - Positive straight-leg raising or femoral stretch test

- Alteration of deep tendon reflexes (knee and ankle)
- Sensory, or motor deficits in the lower extremities.
- Abnormalities in physical examinations
- Number of subjects who experienced any AEs defined as a halting rule
- Serum anti-KTP-001 antibody analysis by electrochemiluminescence

#### **6.7.1.1 Adverse events**

Adverse events (AEs) will be collected from the time of first dose until the last study visit or premature discontinuation of the study drug KTP-001. All (both serious and non-serious) AEs must be followed until they are resolved or stabilized, or until all attempts to determine resolution of the event are exhausted.

All AEs will be coded using the latest version of MedDRA. The frequency of AEs will be tabulated by system organ class and preferred term. The maximum intensity and frequency of AEs will be summarized by treatment.

A treatment-emergent AE (TEAE) is defined as an AE that was not present prior to treatment with study drug, but appeared following treatment or was present at treatment initiation but worsened in severity during treatment. An AE that was present at treatment initiation but resolved and then reappeared while the subject was on treatment will be considered a TEAE (regardless of the intensity of the AE when the treatment was initiated).

All TEAEs will be tabulated according to MedDRA by system organ class and preferred terms. Adverse events table will be summarized for

- Overall summary of adverse events, it includes number of treatment-emergent adverse events, subjects with any TEAE, subjects with any TE- serious adverse events (SAE), subjects with TEAEs leading to discontinuation, subjects with any related TEAE, subjects with any severe TEAE
- Summary of adverse events by system organ class and preferred terms
- Summary of SAEs by system organ class and preferred terms
- Deaths or discontinuations due to AEs (including subjects who have lumbar surgery) that occur after administration of study drug by system organ class and preferred terms.
- Summary of TEAEs by system organ class and preferred terms
- Summary of drug-related TEAEs by system organ class and preferred terms
- Summary of severe TEAEs by system organ class and preferred terms
- Summary of drug-related TEAEs by system organ class and preferred terms
- Adverse events of special interest (AESI) by system organ class and preferred terms

The following AEs will be considered an AESI

1. MRI or X-ray findings of Modic changes, reduction of disc height, or evidence of lumbar instability as defined in [Appendix 4](#), or any other acute MRI or X-ray changes from baseline images deemed significant by the central reader/spine imaging specialist.
2. Exacerbation of back or leg pain meeting at least 1 of the following criteria:
  - a) increase in average daily leg or back pain score by  $\geq 3$  to 6 or above on the numerical rating scale for at least 5 days out of a week
  - b) increase in average daily pain level associated with a new onset of focal neurological symptoms such as numbness and/or tingling or weakness lasting for  $> 5$  days.
3. New onset of neurological symptoms associated with objective changes on neurological examination (weakness, sensory deficit, changes in deep tendon reflexes) whether or not associated with increase in pain level.
4. Any deterioration of subject's condition that in the investigator's judgment requires:
  - a) emergency MRI
  - b) epidural steroid injection/selective nerve root block, facet block, or surgical intervention.

All AEs, SAEs and deaths will be listed.

